**e. Participant recruitment, retention, and withdrawal:**

1. For Objectives 1 - 3:

Recruitment:

Health care workers (intervention, survey, in-depth interviews): The study team will perform information sessions at the health facility to explain the study. We will request to the head clinician that all health care workers attend to ensure everyone has a chance to learn about the project. If the health care worker is interested in participating, their informed consent will be obtained by a study assistant at the health facility or in a location of their preference. For the intervention and survey, we will recruit at convenience, and enroll all interested and eligible participants. For the in-depth interviews (Objective 1) that will be conducted within one month of the completion of sessions, we will attempt to enroll an equal number of HCW by facility and sector, so we will use purposive sampling to select individuals we believe can add varying views to the study findings. Health care workers can withdraw at any time without impact on their clinical position. For the in-depth interviews (Objective 3) related specifically to HCWs' perspectives and experiences of moral injury/ moral trauma, we will contact HCW who had consented to enrollment in the study at intervention sites. For the depression/anxiety surveys that will occur approximately 10-11 months after the intervention, we will also contact HCW who consented to be enrolled at both intervention and control sites and will re-consent HCW. We will inform them of the opportunity to participate in one additional interview or survey and explain the objective of this interview. If the HCW is interested in participating, their informed consent will be obtained by a study assistant at the health facility or in a location of their preference. For this interview with a sub-set of the intervention participant population, we will attempt to enroll an equal number/ proportion of HCW by sex, by health facility, and by category/clinical role of HCW, using purposive sampling to select individuals

we believe can add varying views to the study findings. These HCW can withdraw at any time without impact on their professional position.

People living with HIV (survey): The study team will recruit participants to complete the baseline and endline surveys at the time the individuals are leaving an appointment for HIV care at one of four eligible health care facilities. Recruitment will be done using convenience sampling when the individual exits the health facility after receiving care. If the individual is interested in participating in the study, a study assistant will bring them into a private room to discuss their eligibility and study procedures (complete surveys at study baseline or endline, i.e., 6 months after the study begins, and to the use of a subset of data from their medical records regarding ART medication pick-up history within the previous 6 months). If eligible and they agree to participate, their informed consent will be obtained by the study assistant at the health facility. Participants can withdraw at any time without impact on the clinical care they are receiving.

People living with HIV who are followed as part of routine care (estimated n=16,000): The study team will not formally recruit and consent these individuals to participate in the study, as only a chart review will be performed. For the inclusion of these individuals' data, we will seek a waiver of informed consent, to be developed and included in the submission to the ethics committees/Institutional Review Board (IRB), to access their retention data and viral load results over the course of the study.

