## 6. Design and Study Questions

We propose to conduct a pilot cluster randomized controlled trial to evaluate the effects of our interventions. Four health care facilities in Zambézia Province will be selected and then randomized to the control (standard-of-care [SOC]) or the intervention arms (anti-stigma training ONLY, resilience training ONLY, or anti-stigma + resilience trainings) (i.e., there will be one control arm and three intervention arms).

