## **Procedures for Patients living with HIV**

### *Procedures for PLHIV who have agreed to participate in the survey.*

Survey administration with PLHIV participants enrolled in the study will be completed at two time points: one at baseline (i.e., study initiation) and one at endline (i.e., at 6-7 months after study initiation), including sociodemographic data and three questionnaire components related to: Medical Mistrust, Patient Satisfaction, and Perceived stigma from Health care Providers (**Appendix 2**). The survey will be done at the health facility or at a location suggested by the participant as per the participant's preference, at a location where privacy can be guaranteed as much as possible with the support from a surveyor who is fluent in Echuabo (local language). Participants may be recruited for more than one survey time point, however, different PLHIV participants can be recruited at the two time points. Participants will be requested to allow the use of the Moral Trauma Protocol, Version 1.3; PI: [name], 27 September 2024

of a subset of data related to their ART medication pick-up history for the past 6 months will be collected from their medical records for use in analyzing the survey data (**Appendix 10**). These data will be extracted from the electronic patient tracking system OpenMRS™, which stores clinical information from the medical records of PLHIV registered at the health facility.

*Procedures for PLHIV for whom we will collect routine clinical data.*

We intend to collect demographic and clinical data from patients' medical records that include, but are not limited to: HF, NID, age, sex, level of education, marital status at enrollment in HIV care, date of enrollment in HIV care, date of ART initiation, ARV, Body mass index (BMI), CD4+ T-cell count, HIV-1 viral load (VL) (data and value), WHO clinical stage at the first visit and ART initiation, hemoglobin and full blood count on the date of enrollment in HIV care (or nearest), residence (urban or rural), and records of ART pick-ups (to assess retention) (**Appendix 9**). Data will be extracted from the electronic patient tracking system OpenMRS, that stores clinical information from the medical records of PLHIV registered at the health facility.

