## **Data Analysis**

### **Objective 1:**

#### Quantitative Data Analysis

We will first conduct descriptive analyses. Our psychological and psychosocial measures are continuous or pseudo-continuous (e.g., sums of Likert-style questions) variables. Our outcomes

will be changes in psychosocial measures from baseline to follow-up. Descriptive analyses will include boxplots and summary measures by intervention arm (4 groups). Our formal analyses (those that test hypotheses) will take advantage of the factorial nature of this pilot cluster randomized control trial. These analyses will group together sites as receiving resilience intervention (yes vs. no) and receiving anti-stigma intervention (yes vs. no); therefore, results from two sites will be compared with results from two other sites. This gives us a larger sample size for each comparison and allows us to fit linear mixed effects models that include random effects to account for the correlation between measurements taken from participants at the same site while ensuring that the fixed effect of the intervention is identifiable. We will report results from models that are unadjusted and adjusted for a small number of HCW-level baseline covariates (age, sex, HCW role, and baseline measures of the outcome). Model diagnostics will be performed and outcome variables will be transformed, if necessary, to meet model assumptions.

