## **14. Budget**

	unit cost	#	units		
HUMAN RESOURCES					
Research officer	MZN 50,000.00	1	7	MZN 350,000.00	\$ 5,556
Research assistants (surveyors)	MZN 20,000.00	2	8	MZN 320,000.00	\$ 5,079
TRAVEL & TRANSPORT					
MPT staff travel to Quelimane					

Travel to Quelimane from Maputo (2ps C-Saúde + 1 MOH); 2 trips	MZN 40,000.00	3	2	MZN 240,000.00	\$ 3,810
Per diem Maputo teams on professional travels in MPT/QUEL	MZN 1,400.00	2	12	MZN 33,600.00	\$ 533
Accommodation Maputo teams on professional travels in MPT/QUEL	MZN 5,000.00	2	12	MZN 120,000.00	\$ 1,905
Per diem MOH staff to Zambezia	MZN 6,000.00	1	12	MZN 72,000.00	\$ 1,143
Per diem DPS staff to sites for supervision	MZN 6,000.00	1	10	MZN 60,000.00	\$ 952
Transport interviewers to sites	MZN 9,800.00	1	30	MZN 294,000.00	\$ 4,667
TRAINING/PROJECT ACTIVITIES					
Training Sessions in Intervention Sites					
Food incentives for trainees	MZN 240.00	10	5	MZN 12,000.00	\$ 190
Training Materials	MZN 15,000.00	1	1	MZN 15,000.00	\$ 238
Incentives for MISAU Psychologists					\$ -
Training stipend/per diem	MZN 850.00	1	5	MZN 4,250.00	\$ 67
OTHER					
Tablets	MZN 21,000.00	1	4	MZN 84,000.00	\$ 1,333
Bioethics Review Fees	MZN 20,000.00	1	1	MZN 20,000.00	\$ 317
Transcription of interviews	MZN 3,000.00	1	30	MZN 90,000.00	\$ 1,429
Translation of protocol/ interviews	MZN 20,000.00	1	1	MZN 20,000.00	\$ 317
Surgical Masks	MZN 50.00	1	400	MZN 20,000.00	\$ 317
Snack for sessions	MZN 240.00	400	3	MZN 288,000.00	\$ 4,571
TOTAL COSTS				MZN 2,042,850.00	\$ 32,426

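### Patients for the satisfaction, mistrust and perceived-stigma surveys are recruited by convenience at the exit, with no approach rule or log, so selection can differ by arm or wave and distort these outcomes

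*Combined protocol and SAP*

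**What the plan says.** Section 7.e (recruitment of people living with HIV for the survey) sets the method for both waves: "Recruitment will be done using convenience sampling when the individual exits the health facility after receiving care". Entry then depends on the patient's interest: "If the individual is interested in participating in the study, a study assistant will bring them into a private room", where eligibility is checked and consent taken. Section 8.a adds that "different PLHIV participants can be recruited at the two time points", and that the interview is done "with the support from a surveyor who is fluent in Echuabo". No section gives a sampling interval, a consecutive or random rule, survey days or hours, or a record of people approached, ineligible or refusing.

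Section 6 states that "there will be one control arm and three intervention arms", with four facilities in total, so each arm is a single site. Section 7.c plans 80 surveys per facility (320 in all), from facilities with at least 4,000 patients on ART. It calls the survey exploratory, but also states 80% power for differences of 0.55, 0.71 and 0.96 SD at ICC 0.025, 0.05 and 0.10.

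Satisfaction at 6 months is part of Hypothesis 2 (section 5). The timeline (section 15) says the surveys are to assess the impact of the interventions on mistrust, satisfaction and perceived stigma.

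**The concern.** The survey asks patients to rate their care, and they are recruited just after receiving it. About 80 of at least 4,000 patients per site are surveyed (80/4,000 = 2% at most), so the result depends heavily on who is approached and who agrees. Nothing in the plan fixes either.

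With one facility per arm, site and arm are the same thing. At endline, respondents are recruited after allocation and after training. If recruiters at a trained site tend to stop patients who look content, or if patients there are more willing to talk when pleased, the arms differ for reasons unrelated to training. The opposite pattern would hide a real effect. Because nobody records who was passed over or refused, the analyst cannot describe the selection afterwards, let alone correct it. Section 12 says the pilot's data will inform a fully powered trial, so a selection artefact could be carried into that design.

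**Working it through.** **Inputs from the documents.** 80 respondents per facility and ICC 0.025 / 0.05 / 0.10 (section 7.c). Two-sided alpha of 0.05, stated in 7.c for the chart-review calculation and applied here. Factorial comparison, in which "results from two sites will be compared with results from two other sites" (section 10, Objective 1; Objective 2 follows the same approach). Each comparison is therefore 160 versus 160.

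**Step 1: reproduce the plan's figures.** Design effect DE = 1 + (80 − 1) × ICC; effective total N = 320/DE; SE of the difference in SD units = √(2 × DE/160); detectable difference by normal approximation = (1.960 + 0.842) × SE. The t version uses the noncentral t with effective N − 2 degrees of freedom.

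| ICC | DE | Effective N | SE | Detectable, normal | Detectable, t | Stated |
|---|---|---|---|---|---|---|
| 0.025 | 2.975 | 107.6 | 0.193 | 0.540 | 0.545 | 0.55 |
| 0.05 | 4.95 | 64.6 | 0.249 | 0.697 | 0.708 | 0.71 |
| 0.10 | 8.90 | 36.0 | 0.333 | 0.934 | 0.962 | 0.96 |

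The stated figures are reproduced by the t version. They contain no allowance for selection bias.

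**Step 2: shift in one site's mean (assumed inputs).** If a share p of a site's respondents is replaced by patients scoring g SD better, the site mean rises by p × g. The documents give neither p nor g. With g = 0.8 SD, p = 0.10 gives 0.10 × 0.8 = 0.08 SD and p = 0.30 gives 0.30 × 0.8 = 0.24 SD.

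**Step 3: carry the shift into the factorial contrast.** For resilience, the yes side is {resilience only, both} and the no side is {control, anti-stigma only}. One site on the no side is also trained. If all three trained sites shift by d, the yes side moves by d and the no side by d/2, so the contrast moves by d − d/2 = d/2. The anti-stigma contrast works the same way. The shift is:

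- 0.08/2 = 0.04 SD to 0.24/2 = 0.12 SD;
- 0.04/0.71 = 6% to 0.12/0.71 = 17% of the stated detectable difference at ICC 0.05.

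Only if selection acts at both sites on one side of the margin and at neither on the other does the contrast move by the full 0.08-0.24 SD (11-34% of 0.71).

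**Step 4: effect on the test with no true effect.** For a contrast shift b, P(p < 0.05) = Φ(−1.96 + b/SE) + Φ(−1.96 − b/SE), by normal approximation, against a nominal 5%.

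| Contrast shift b (SD) | ICC 0.025 | ICC 0.05 | ICC 0.10 |
|---|---|---|---|
| 0.04 | 5.5% | 5.3% | 5.2% |
| 0.12 | 9.5% | 7.7% | 6.5% |
| 0.24 (one side only) | 23.8% | 16.2% | 11.1% |

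**Step 5: do the existing safeguards close the gap?**

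- The eligibility criteria (7.b) define who may enter, not who is approached.
- The aim of similar proportions by sex and sector (7.d) has no quota or procedure.
- The planned covariates (section 10, Objective 2) are age, sex, education, marital status, language, time on ART and past pick-ups. None measures how satisfied a person is on leaving.
- The baseline wave removes selection that works alike at both waves. It is not a within-person control, because different people may be surveyed. Baseline recruitment (months 1-2) also overlaps the training sessions (months 1-4) in section 15.

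**The case against.** The strongest reply is that the survey is a minor part of a four-site pilot whose limits the protocol admits. Section 8.b makes chart-based adherence, retention and viral load the primary patient measures, and these take all eligible patients. The survey size is called exploratory, and Hypothesis 2 names satisfaction but not mistrust or perceived stigma. There are eligibility criteria, a sex and sector aim, a baseline wave and covariate adjustment. All of this stands: it limits the scope of the point and makes the safeguards partial rather than absent.

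Two stronger readings are tempting and are not supported. A reader might infer that respondents are hand-picked. Section 7.e describes convenience recruitment of patients who express interest, and the protocol reserves purposive sampling for the health care worker interviews. Patient self-selection is as plausible a route to bias as recruiter choice.

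A reader might also infer that recruiters cannot be blind. The documents say nothing on masking. The budget's line for "Research assistants (surveyors" lists two people and is separate from the psychologists' line, and nothing says that the surveyors deliver training or alone decide whom to approach. Knowledge of the arm is probable with one site per arm, but it is not established. At baseline it is less certain still, because the documents do not say whether randomization comes before that wave.

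What remains is that the selection rule is undefined and unlogged, and at endline it operates after allocation and after the rated visit.

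**Conclusion.** The point holds for the patient survey outcomes only. Convenience recruitment at the exit, with no approach rule and no log, allows selection to differ by arm or wave, and the planned safeguards reduce this only in part.

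On the illustrative inputs (10-30% replacement, a 0.8 SD gap, all three trained sites affected), the bias in a factorial contrast is 0.04-0.12 SD. That is modest beside the stated 0.71 SD and raises the false-positive rate at ICC 0.05 from 5% to at most 7.7%. It reaches 0.24 SD and 16.2% only if selection acts on one side of the margin. The same shifts in the other direction would mask a true effect. The replacement share and the gap are assumptions, and the documents do not show that such selection will occur. The case for change is that the gap is cheap to close before data collection and cannot be repaired afterwards.

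**What to change.** In section 7.e, replace convenience sampling with one rule that leaves the recruiter no choice, used identically at all four sites and both waves:

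- Set survey days and hours in advance and rotate them across the HIV care sectors (adult care, ANC, CCR, TB/HIV).
- Each time a surveyor becomes free, they approach the next adult PLHIV leaving an HIV care appointment, until 80 per site are reached.
- In mixed services such as ANC, the way patients are identified must not disclose HIV status.
- Keep an anonymous tally of those approached, ineligible and refusing, and report it by site and wave.

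A next-patient rule suits surveyors who also conduct the interviews. Counting every kth exit across several sectors would be hard for them, and at ANC exits could reveal HIV status.

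The cost is protocol wording, a tally sheet and slightly slower accrual. No extra staff or patients are needed, and the 80 per site and the stated detectable differences are unchanged. The rule does not remove refusal or interviewer effects, but it makes refusal visible.

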#### Retention in the Study:

Health care workers who agree to participate in the training program will be encouraged to complete all sessions. During each session, a snack will be offered, as sessions will occur in the afternoon. Additionally, a certificate of completion for those who participate in each session will be provided, and there will be the option for those who complete all the intervention sessions to be first in line for any subsequent training of trainers sessions to lead future groups at each facility. Related to retention to study activities, specifically the survey and/or in-depth interview activities, our study personnel will ask for permission to reach out to participants via phone (call and/or text) if they miss their study-related data collection appointment. This number will be destroyed when the study finishes.

#### Withdrawal from the Study

[figure not shown]
Health care workers and PLHIV can withdraw from the study at any time without consequence. If a participant wishes to withdraw, we would ask for them to communicate with our study manager.

## 8. Methods

### a. Study Procedures

**Objective 1:** Resilience Intervention and Anti-Stigma Intervention on health care worker behavior

We will assess the success of each element of the multi-component intervention with a pilot cluster randomized controlled trial (RCT) at four health facilities (see **Figure 1**). Although a fully powered cluster RCT with multiple health facilities randomized to each arm is outside the scope of this study, the delivery of a health care worker team wellness intervention requires a health facility-based approach.

**Figure 1:** Study Design

### Intervention designs

All intervention sessions (wellness/resilience-related and burnout-related) will offer a didactic (educational) component and a practical (e.g., interactive) component to allow for participants to learn about the session topic(s) and to practice the skills and activities discussed/proposed in a dedicated time/space with support from session facilitators.

#### Wellness and Resilience Intervention

Health care workers working at sites randomized to resilience training or the combination anti-stigma and resilience training will receive a group-based Mindfulness-based Wellness and Resilience (MBWR) intervention. The training course will occur every other week and consist of 4 sessions of 60-120 minutes each. The day and time of the intervention session will be determined by health facility staff to facilitate attendance. We will focus on common challenges encountered in the health facility, as well as coping strategies, and future goals to improve provider well-being.

The team selected a group-based, mindfulness-based wellness and resilience (MBWR) intervention. MBWR is designed to be a brief, cost-effective, evidence-based, and replicable intervention to enhance resilience and self-compassion among teams providing primary health care services. The training is based on an established Mindful Practice curriculum^63 and Mindfulness-Based Stress Reduction curriculum. This intervention was selected because it focuses on developing resilience and self-care at the team level (which is how HIV care and treatment is delivered) and because the training can be conducted by a trained Bachelor-level psychologist. The original training course consists of weekly sessions of 60-120 minutes each over 6-10 weeks. Our team has adapted the curriculum to include common challenges encountered in these health facilities, facility-level strategies that can empower health care workers to improve conditions, individual coping strategies, and future goals to improve HCW well-being (see **Table 2**).

**Table 2:** Adapted Wellness and Resilience Training Topics

Focus of Resilience Training Sessions	Intended Learning outcomes
1) Burnout and its consequences and ways to respond/ when to seek care	
 
Factors that may lead to the feeling/ experience of burnout;
 
Understand the signs and symptoms of burn-out and the consequences of not-identified burn-out among health care workers;
 
Getting skills to help colleagues in identifying symptoms;
 
Know how to recognize burnout and where to refer to if experiencing symptoms;
 
Interactive component: share ways that burnout impacts either yourself or colleagues who you work with.
 

2) Self-care and ways to cope with work-related stressors & Teamwork and social support	
 
Getting coping strategies skills to overcome some work-related stressors;
 
When and how to seek care from others/ a professional;
 
Interactive component: practice examples of self-care (e.g., meditation, breathing exercises, etc.).
 
Understand the importance of teamwork/ social support in the prevention of work-related stress and in the provision of better patient care;
 
Interactive component: brainstorming ideas for social support/group activities that could be supported by and/or at the workplace.
 

3) Communicating and managing interpersonal relationships with others (ex. colleagues, patients, etc.), conflict handling in the work setting	
 
How to better communicate with others in the workplace and resolve work setting conflicts;
 
Ways to advocate for self and communicate expectations among team members;
 
Interactive component: what options for improving communication and/or interacting with others might work at your facility; role play with other participants to practice navigating difficult conversations (e.g., in pairs, could share with larger group).
 

4) Finding better balance between life and work activities/responsibilities	
 
Describe responsibilities that one may juggle between life and work;
 
Discuss ways to build healthier balance in work and life activities/priorities;
 
Interactive component: pairs or small group discussions for personal experiences of 'juggling' responsibilities, brainstorming ways to have better balance.
 

